#### **C.4. Study Procedures:**

**Educational Intervention group:** The 20 patients randomized to the SLT Educational Intervention group will meet with their ophthalmologist who will discuss both SLT and medication options for treatment of glaucoma, which is currently standard of care. After their eye exam, the patient will meet with the research coordinator. The research coordinator will then ask the patient questions to assess their knowledge, beliefs, barriers, and attitudes about SLT vs. medication as first line treatment of glaucoma (See section D.2.a). The patient will then review the SLT Educational Intervention and be shown the PowerPoint presentation about SLT. After the presentation, the patient will be asked more questions (See section D.2 b). After viewing all information, the Intervention patient will have the opportunity to ask questions to the research coordinator about SLT. If the patient elects to schedule an SLT after the Educational Intervention, they will be assisted with making this appointment.

**Usual Care group procedures:** The 20 patients randomized to the Usual Care group will meet with their ophthalmologist who will recommend both SLT and medication options for treatment of glaucoma, which is currently standard of care. After their eye exam, the patient will meet with the research coordinator who will answer any questions they have about treatment options. The research coordinator will then ask the patient questions to assess their knowledge, beliefs, barriers, and attitudes about SLT vs. medication as first line treatment of glaucoma (See section D.2.a). The Usual Care group will not be exposed to SLT Educational Intervention and will not be asked to watch a video about SLT. If the patient elects to have SLT at any point during the study, we will provide the phone number for them to schedule the procedure. Patients in the Usual Care group will not be assisted with making any SLT appointments.

If patients in either group would like to consult with their ophthalmologist again, we will provide a message to the physician and he/she will call the patient to discuss treatment options again. Doctors will be masked to the group assignment to reduce biasing the outcome. We will track how many patients wanted to speak to their ophthalmologist over the phone or in person in both groups and the outcome of these calls.

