**D.2.a. Questions for Patients in Both Groups after Consenting and Eye Exam**

Are you aware that glaucoma can be treated with laser therapy instead of eye drops?  
Did you know that laser therapy is a possible first option for treating glaucoma before eye drops?  
Did you discuss laser therapy with your glaucoma doctor today?  
Would you consider having laser treatment? Why or why not?  
Would you consider having this laser therapy instead of filling your prescription for eye drops?  
If no, please describe reasons.

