**D.2.b. Questions for Intervention Patients After Viewing the Presentation and Video**

Did you have any questions about the educational program we showed you?  
Would you consider having laser therapy to treat your glaucoma?  
Would you consider having this laser therapy instead of filling your prescription for eye drops?  
If no or maybe, let's discuss why?  
If yes, can I help you to schedule a laser appointment at your convenience?

In order to assess the beliefs and attitudes of a group of ophthalmologists about SLT as first line therapy before and after viewing Educational Intervention, we will ask the following questions to determine how they approach newly diagnosed patients with glaucoma.

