**D.2.d. Ophthalmologists' Questions After Viewing the Presentation and Video:**

- 1) Did this educational program convince you that SLT is appropriate as first line therapy instead of medication? Why or why not?
- 2) If you are reluctant to recommend SLT as first line therapy, please explain why.
- 3) What additional information would you like to know to help make an informed decision?

**E. Study Timeline:** The study will be conducted between July 1, 2017 and June 31, 2018. We will complete all IRB submission and staff training prior to July 1, 2017. We will develop the Educational Intervention and video during the initial 3 months of funding period. We will identify, recruit, consent and enroll 40 patients, who will be randomized, 20 to the Educational Intervention group and 20 to the Usual Care group between August 1, 2017 and January 30, 2018. Data cleaning, analysis, and dissemination of findings will be completed by June 30, 2018 and a dissemination plan will be implemented to include submitting publication and

abstracts for presentations at national research meetings such as American Glaucoma Society and American Academy of Ophthalmology.

**F. Statistical Analysis:** All data analyses will be conducted using R (R core team, Vienna, Austria). Fisher's exact test for count data will be used to compare the pre- and post-SLT Educational Intervention survey answers. Descriptive statistics will be used to present patient demographic and clinical data.

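### Section F plans Fisher's exact test, which assumes independent groups, for before/after survey answers that come from the same 20 intervention patients

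*Combined protocol and SAP*

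**What the plan says.** Section F names one inferential test: "Fisher's exact test for count data will be used to compare the pre- and post-SLT Educational Intervention survey answers". It does not say whose answers are meant, and neither it nor any other section names a paired method or says that a respondent's two answers will be linked.

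Section C.4 sets the order of events for the intervention group. After the eye exam the coordinator asks the D.2.a questions and shows the presentation, and then: "After the presentation, the patient will be asked more questions" (D.2.b). For the other arm: "The Usual Care group will not be exposed to SLT Educational Intervention and will not be asked to watch a video about SLT". Usual Care patients answer D.2.a only.

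One item appears in both D.2.a and D.2.b with the same wording: "Would you consider having this laser therapy instead of filling your prescription for eye drops". A second is close: "Would you consider having laser treatment? Why or why not" in D.2.a and "Would you consider having laser therapy to treat your glaucoma" in D.2.b. No response options are listed. The follow-up prompts hint that they may differ: "If no, please describe reasons" before, "If no or maybe, let's discuss why" after.

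Section D.1.a makes beliefs and attitudes before and after viewing the secondary outcome, for patients and for ophthalmologists.

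**The concern.** Every patient answer given after the presentation comes from someone who answered before it, minutes earlier. The question is whether individuals changed their minds, and the information on that lies in the switchers: no to yes, and yes to no. Fisher's test on before and after counts uses only the two totals and assumes that the two sets of 20 answers come from different people.

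If a patient's two answers are positively correlated, the test overstates the uncertainty of the change and can miss a real shift. What is at stake is the patient part of the secondary outcome.

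**Working it through.** **Inputs from the documents.** There are 20 intervention patients (C.3, C.4), each answering before and after; one item is identical and one near-identical (D.2.a, D.2.b). The plan states no alpha, power, expected response rate or correlation, so it has no figure to reproduce.

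**Assumptions.** Yes/no answers, two-sided 0.05, and the response rates and within-patient correlations (phi) shown below.

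**Could another reading make Fisher's test fit?**
- All 40 before answers against 20 after answers: the same 20 people are still on both sides.
- Cross-tabulating before by after within patients: Fisher's test then assesses association between the two answers, not change.
- Comparing the arms after the presentation: impossible, because Usual Care has no such answers.

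**Worked example: 8/20 yes before, 14/20 yes after.** Fisher's test on the table (8, 12; 14, 6) gives p = 0.111, whoever switched. Exact McNemar uses b patients switching to yes and c switching back, with p = 2 × Σ C(b+c, k) × 0.5^(b+c), summed over k = 0 to min(b, c):

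| To yes / back | Calculation | p |
|---|---|---|
| 6 / 0 | 2 × 1/64 | 0.031 |
| 7 / 1 | 2 × (1+8)/256 | 0.070 |
| 8 / 2 | 2 × (1+10+45)/1024 | 0.109 |
| 9 / 3 | 2 × (1+12+66+220)/4096 | 0.146 |

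All four patterns have the same totals, yet the evidence for change differs widely.

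**Confidence interval for the 30-point change.** Newcombe's method combines the Wilson limits for 8/20 (0.219 to 0.613) and 14/20 (0.481 to 0.855). The lower limit is 0.30 − √[0.219² − 2φ(0.219)(0.213) + 0.213²], where 0.219 = 0.700 − 0.481 and 0.213 = 0.613 − 0.400; the upper limit is formed likewise.
- Unpaired (φ = 0): −0.6 to 53.8 points.
- Paired, 6 and 0: continuity-corrected φ = (8×6 − 0×6 − 10)/√(8×12×14×6) = 38/89.8 = 0.423, giving 6.8 to 48.2 points.
- Paired, 9 and 3: φ = (5×3 − 3×9)/89.8 = −0.134, giving −2.6 to 55.3 points.

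This interval and the exact test can disagree near 5%. With 7 and 1 the interval is 2.7 to 51.3 points while p = 0.070.

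**Power, by full enumeration of the multinomial for 20 pairs.** Reversals are the proportion moving from yes to no.

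| Shift in yes | Reversals | phi | Fisher | McNemar |
|---|---|---|---|---|
| 40% to 70% | 0 | 0.53 | 28% | 58% |
| | 5% | 0.31 | 32% | 45% |
| | 10% | 0.09 | 34% | 37% |
| | 12% | 0 | 35% | 34% |
| 30% to 50% | 0 | 0.65 | 6% | 20% |
| | 5% | 0.44 | 10% | 20% |
| | 10% | 0.22 | 13% | 17% |
| 50% to 80% | 0 | 0.50 | 36% | 58% |
| | 5% | 0.25 | 39% | 45% |
| | 10% | 0 | 41% | 37% |

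**Type I error with no true change, 40% yes.**

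| phi | Fisher | McNemar |
|---|---|---|
| 0.58 | 0.1% | 0.5% |
| 0.38 | 0.5% | 1.3% |
| 0 | 2.4% | 2.2% |
| −0.25 | 4.3% | 2.4% |
| −0.46 | 6.1% | 2.6% |
| −0.67 | 7.8% | 3.0% |

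**Ophthalmologists.** Section C.6 cites D.2.c for the survey completed after viewing, whereas the D.2.c heading places those questions before viewing. Under the D.2.c and D.2.d headings no item is repeated, so no item-level before/after test can be run. If C.6 governs and D.2.c is also asked at the interview, the pairing problem arises there too.

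**The case against.** The harm rests on assumed inputs, and the largest gain belongs to the case with no reversals. For the 40% to 70% shift, the advantage of the paired test falls from 30 points (58 − 28) to about 14 with 5% reversals and about 3 with 10%. At zero correlation Fisher's test is level or slightly ahead. This stands, and it is why the result is given as a range. On the other hand, few reversals are plausible minutes after a presentation that favours SLT.

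Only one or two patient items are repeated, and D.1.a says the questions may still be revised with a survey specialist. That limits the reach of the problem. It does not make the planned test suitable, because Section F does not tie the choice of test to that revision.

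The likely error is conservative, and nothing in the plan makes trial success depend on it. This holds for positive or zero correlation. Fisher's test exceeds 5% only at clearly negative correlations (6.1% and 7.8% above), which are implausible for answers given minutes apart.

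The ophthalmologist conflict may be no more than a wrong cross-reference, with D.2.d intended. That is a fair reading, so it is a side point here.

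**Conclusion.** The concern holds. The only inferential test in the plan does not match the patient data it is meant to analyse: the two sets of answers are paired and the test assumes that they are not. This is a wrong choice as written, not a missing detail.

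The size is uncertain. Under the assumptions above, the paired test gains up to 30 points of power when answers are strongly correlated and few patients reverse, and nothing when answers are uncorrelated. False positives are not inflated under positive or zero correlation. The consequence is modest, because it touches one or two items within the secondary outcome of a 40-patient pilot and leaves the primary outcome, completed SLT, unaffected. The plan should still be corrected, since doing so costs almost nothing.

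**What to change.** **Patients.** Replace the Fisher sentence in Section F with text along these lines: *Patient items asked both before (D.2.a) and after (D.2.b) the presentation will be compared in intervention patients with both answers, linked by study ID, using the exact McNemar test if answers are recorded as yes/no, or a paired ordinal method if recorded as yes/maybe/no. The paired change will be reported with a 95% confidence interval.* Record the same response options at both points, and word the near-identical item the same in both lists so that it can be used as well. The documents mention no study ID; any identifier that joins a patient's two sets of answers will do, and one coordinator asks both sets.

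**Ophthalmologists.** First reconcile Section C.6 with the D.2.c heading on when those questions are asked. Then either repeat at least one identical closed item with linked responses and use a paired test, or state that these answers will be reported descriptively.

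**Cost.** For patients: two sentences in Section F, aligned wording and response options, and the linkage, with no extra data collection. For ophthalmologists: one corrected cross-reference and, only if a test is wanted, one repeated closed item with an identifier carried from the interview into the online survey.
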